- **GMFR:** The geometric mean fold ratio = antilog (LSMeans [log10 y]), where y is the assay fold ratio and LSMeans is the least square means calculated by the model.
- **4-fold increase:** A subject achieved 4-fold increase if fold ratio ≥ 4
- **BLQ:** Below lower limit of quantification (LLOQ). Per Center for Biologics Evaluation and Research (CBER) criterion, BLQ titer/concentration will be analyzed as:
 - 0.5*LLOQ for calculations of GMT/GMC and GMT/GMC Ratios (GMRs)
 - 1*LLOQ for calculations of fold ratio.
- **ULOQ:** Upper limit of quantification. Titer/Concentration above ULOQ will be analyzed as:
 - 1*ULOQ for all calculations (GMT/GMC, GMRs, fold-ratio)

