6.6.1. GMT/GMC, GMR and GMFR

To estimate the immunogenicity response 1 month first vaccination, OPA titers (log10) and IgG titers (mcg/mL) measured at Day 29 visit will be logarithmically transformed for analysis and GMTs/GMCs will be computed with 95% CI for each assay using ANOVA and ANCOVA.

[figure not shown]
- [S] [E] First model in an ANOVA with log10-transformed concentrations/titers at Day 29 as the dependent variable and treatment group and study site as the fixed effects in the model. Bar plots of OPA GMT, IgG GMC and their 95% CI computed by this model will be created for the full IEP only.
- [S] [E] Second model in an ANCOVA with log10-transformed concentrations/titers at Day 29 as the dependent variable, treatment group and study site as the fixed effects and log10 baseline concentration/titer as the covariate

The least squares means, and their 95% CIs calculated based on the ANOVA and ANCOVA will be back transformed and reported as the group GMT and GMC values. Comparisons between relevant groups will be based on the estimated adjusted GMTs measured at Day 29 visit for 24 serotypes in VAX-24 (of those 20 in PCV20), and mean square error calculated from the basic ANOVA model using contrast statements. The main comparison of interest will be the three VAX-24 dose levels group versus the PCV20 (20 serotypes) group. However, the three VAX-24 dose groups will also be compared in a pairwise fashion on a serotype-by-serotype basis. No adjustment for multiplicity will be applied and missing data will not be imputed. GMRs will also be calculated from the ANCOVA and ANOVA models.

The analysis of GMFR at Day 29 relative to Day 1 will also be computed using similar models:

- [E] First model in an ANOVA with log10-transformed fold ratio at Day 29 as dependent variable and treatment group and study site as the fixed effects in the model. A Forest Plot summarizing the results by serotype of this model will be created for OPA on the full IEP only.
- [E] Second model in an ANCOVA with log10-transformed fold ratio at Day 29 as dependent variable, treatment group and study site as the fixed effects and log10 baseline concentration/titer as the covariate

The least squares means, and their 95% CIs calculated based on the ANOVA and ANCOVA will be back transformed and reported as the group GMFR value.

[REDACTED]

[REDACTED]

[REDACTED]

[REDACTED]

[REDACTED]

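### Setting every result above the assay's upper limit to that limit can compress the GMRs and narrow their intervals if a material share of Day 29 results exceeds it; a tabulation and a censored sensitivity analysis should be pre-specified.

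*SAP*

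**What the plan says.** SAP 5.2 (Data Conventions) gives rules for results outside the assay range.

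- **Above the range:** "Upper limit of quantification. Titer/Concentration above ULOQ will be analyzed as" "1*ULOQ for all calculations (GMT/GMC, GMRs, fold-ratio".
- **Below the range:** the rule depends on the calculation. It is "0.5*LLOQ for calculations of GMT/GMC and GMT/GMC Ratios (GMRs", and the full LLOQ for fold ratios. The SAP attributes this rule to a CBER criterion.
- **Responder definition:** "A subject achieved 4-fold increase if fold ratio" is at least 4, where the ratio is Day 29 over Day 1. The ULOQ rule applies to this ratio too.

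SAP 6.6.1 then analyses the resulting values as ordinary observations. The basic model is described as "First model in an ANOVA with log10-transformed concentrations/titers at Day 29 as the dependent variable", with treatment and site as fixed effects; the ANCOVA adds log10 baseline. Group comparisons use the "mean square error calculated from the basic ANOVA model using contrast statements". On what is compared, the section says "The main comparison of interest will be the three VAX-24 dose levels group versus the PCV20 (20 serotypes) group", and that "the three VAX-24 dose groups will also be compared in a pairwise fashion on a serotype-by-serotype basis".

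SAP 3.3 lists the Day 29 GMTs and GMCs as secondary endpoints, and the GMR comparison, GMFR and 4-fold percentages as exploratory. Protocol 9.7.1 does not mention ULOQ. The readable text has no censored-data model, no count of results above ULOQ and no sensitivity analysis to this rule. Some SAP immunogenicity text is redacted.

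**The concern.** A result above ULOQ is right-censored: the laboratory knows only that it exceeds the limit. Replacing it with the limit has two effects under the SAP's own model of log10 values with one residual variance. The arm with the higher response has more of its distribution cut back, so the difference in log means shrinks. The upper tail is also compressed in every arm, so the mean square error, and with it the interval, shrinks too. The estimate moves while its stated precision improves.

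The comparisons exposed are the ones the SAP names as of main interest, and the dose-to-dose comparisons in a trial titled dose-finding. Protocol 9.1 also expects the sample to be adequate for planning later studies. A GMR pulled toward 1 and an understated SD would both carry into that planning.

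The cap has a separate effect on responder status. The Day 29 value cannot exceed ULOQ, so a subject whose baseline is above ULOQ/4 has a fold ratio below 4 whatever the true rise.

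**Working it through.** **Inputs from the documents.** The 1×ULOQ rule (SAP 5.2); the linear model on log10 values with a common mean square error (SAP 6.6.1); 200 subjects per arm aged 50 to 64 (Protocol 3.1); two-sided 0.05 (SAP 6.2.1).

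**Assumed inputs.** The documents give no ULOQ, share above it, SD or expected GMR. I take log10 values as normal with SD 0.6 in both arms (range 0.4 to 0.8), 1 to 20% of the PCV20 arm above ULOQ, and true GMRs of 2.0, 1.5 and 0.5. Site and baseline terms are left out.

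The plan has no figure of its own to reproduce here, since Protocol 9.1 gives no statistical basis for the 800 subjects.

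**Formula.** For X normal with mean μ and SD σ, let b = (U − μ)/σ, where U is log10 ULOQ. Then

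E[min(X, U)] = μΦ(b) − σφ(b) + U(1 − Φ(b)),

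with the variance from the matching second moment. The capped GMR is 10 to the power of the difference in capped means. The SE is √((v₁ + v₀)/200), where v₁ and v₀ are the capped variances. Coverage is the normal probability that estimate ± 1.96 SE contains the true log10 GMR.

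**Worked case: true GMR 2.0, 20% of PCV20 above ULOQ.**

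1. Set the PCV20 mean to 0. Then U = 0.8416 × 0.6 = 0.505.
2. PCV20: b = 0.842, capped mean −0.067, capped SD 0.500.
3. VAX-24: μ = log10 2 = 0.301, b = 0.340, 36.7% above ULOQ, capped mean 0.150, capped SD 0.417.
4. Difference: 0.150 + 0.067 = 0.217, so the GMR reads 10^0.217 = 1.65.
5. SE: √((0.500² + 0.417²)/200) = 0.046. Uncapped, it would be 0.6 × √(2/200) = 0.060. The ratio is 0.77.
6. Bias: 0.217 − 0.301 = −0.084, about 1.83 SE. Coverage is 55%.

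**Results, SD 0.6, 200 per arm.** Each cell gives the GMR as read, with coverage of the nominal 95% interval for the uncapped GMR.

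| PCV20 above ULOQ | True GMR 2.0 | True GMR 1.5 | True GMR 0.5 |
|---|---|---|---|
| 1% | 1.97 (95%) | 1.49 (95%) | 0.50 (95%) |
| 5% | 1.89 (93%) | 1.46 (94%) | 0.51 (95%) |
| 10% | 1.80 (86%) | 1.42 (93%) | 0.52 (94%) |
| 20% | 1.65 (55%) | 1.36 (85%) | 0.55 (87%) |

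The PCV20-arm SD falls from 0.600 to 0.574, 0.549 and 0.500 at 5, 10 and 20% above ULOQ, which is 4, 8 and 17%.

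**Sensitivity to the SD.** At a true GMR of 2.0 and 20% above, SDs of 0.4 to 0.8 give readings of 1.60 to 1.67. At 5% above, SD 0.4 is the worst case: the reading is 1.86, with coverage 85%.

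**Where the pattern breaks.**

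- True GMR 1 with equal SDs: the GMR does not shift and coverage stays at 95%, although the SE is still smaller.
- Unequal SDs: with 0.5 for VAX-24, 0.7 for PCV20 and 20% of PCV20 above ULOQ, the capped means are 0.039 and −0.078. A true GMR of 1.20 then reads 10^0.117 = 1.31, which is away from 1.

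**Check of the alternative.** A censored-normal maximum-likelihood model was simulated with 600 runs per scenario, SD 0.6 and 200 per arm. At a true GMR of 2.0 and 20% above, it gave 1.99 with 94% coverage; the capped analysis gave 1.64 with 53%. At 5% above, the figures were 2.00 with 94%, against 1.88 with 92%.

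**The case against.** **The size is wholly assumed.** This stands. If almost no results exceed ULOQ, nothing happens; at 1% the effect is negligible, and at 5% it is small in most scenarios. A reader might infer that the rule does bias this trial's GMRs toward 1 and does make its intervals too narrow. The documents do not support that, because they give no ULOQ, share above it or SD, and even the direction depends on similar SDs.

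**A weak dose is hardly flattered.** This largely stands. A reader might infer that the cap makes a clearly inferior dose look close to PCV20. At a true GMR of 0.5 the reading is only 0.52 with 10% above ULOQ and 0.55 with 20%. The larger distortion comes when VAX-24 is the stronger arm.

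**No decision rule rests on these GMRs.** This also stands. The readable text has no margin or dose-selection rule, and SAP 3.3 makes the GMR exploratory. That limits the weight of the point but does not remove it, because SAP 6.6.1 still calls the VAX-24 versus PCV20 comparison the main one of interest.

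**Silence proves little.** A reader might infer that samples above ULOQ are never re-diluted and retested, or that no sensitivity analysis exists. Neither follows: retesting is laboratory practice, and the SAP contents show redacted entries near 6.2.4 and after 6.6.1. The point therefore rests only on the rule as written.

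**Reverse cumulative curves would show a ceiling.** In part. SAP 3.3 plans them for OPA but not IgG, and a visible ceiling does not correct a GMR.

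**A censored model has costs.** This stands. It relies on log-normality in the unobserved tail, and it does not repair the fold-ratio endpoints or a capped baseline covariate. That argues for running it beside the planned models, not in their place, and for leaving the below-LLOQ rule alone.

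**Conclusion.** The point holds conditionally. Where a material share of a serotype's Day 29 results exceeds ULOQ and the arms have similar SDs, the planned analysis shrinks the GMR toward 1 and gives an interval too narrow for the uncapped GMR. Under log-normality with SD 0.6 and 200 per arm, the effect is serious at about 20% above ULOQ when the GMR is well above 1. It is already visible at 10% when the GMR is near 2, and negligible at about 1%. Which case applies cannot be known from the documents, and that is the reason to measure it and fix the response in advance.

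The consequence is confined to secondary GMT/GMC and exploratory GMR and fold-rise results. The primary safety endpoints are unaffected. This is a worthwhile, inexpensive improvement, not a flaw that invalidates the plan.

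**What to change.** Keep the planned ANOVA and ANCOVA and the below-LLOQ rule. Before the Day 29 interim database lock (SAP 2.7), add to the SAP:

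1. A table of the number and percentage of results above ULOQ by serotype, arm and visit, for OPA and IgG.
2. A right-censored (censored-normal) sensitivity analysis of GMT/GMC and GMR with the same model terms, for any serotype in which more than a pre-set share of Day 29 results exceeds ULOQ in any arm. A share of 5% is a reasonable example. Report it beside the planned result.
3. The number of subjects in each arm with a baseline above ULOQ/4, shown beside the 4-fold results, because those subjects cannot meet the criterion under the cap.

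The cost is some SAP wording, one standard model and a few outputs, with no new samples. The censored estimates depend on log-normality in the upper tail, and the report should say so. Setting the trigger before the lock avoids choosing the method after the results are seen.

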5.3. Methods of Pooling Data

Not Applicable.

5.4. Withdrawals, Dropouts, Loss to Follow-up

Subjects who undergo Early Discontinuation after randomization and before Day 1 vaccine administration may be replaced by randomizing an additional subject at the Sponsor’s discretion. Subjects who undergo Early Discontinuation after study vaccination will not be replaced.

6. STATISTICAL METHODS

6.1. Sample Size Justification

Sample size is not driven by statistical assumptions for formal hypothesis testing.

For subjects 18 to 49 years of age, with 16 subjects, events that occur at a frequency of 15% or more will be detected with at least 92% probability and events that occur at a frequency of 10% or more will be detected with 81% probability. Therefore 16 subjects in each treatment group are proposed as the basis for the number of subjects in whom to conduct the first safety assessment.

6.2. General Statistical Methods

6.2.1. General Methods

All outputs will be incorporated into Microsoft Word files, sorted, and labeled according to the International Conference on Harmonization (ICH) recommendations, and formatted to the appropriate page size(s).

Tabulations will be produced for appropriate demographic, baseline, safety, and immunogenicity parameters. For categorical variables, summary tabulations of the number and percentage within each category (with the number of subjects with missing data) of the parameter will be presented. For continuous variables, the mean, median, standard deviation, minimum and maximum values will be presented.

Formal statistical hypothesis testing will be performed on immunogenicity parameters with all tests conducted at the 2-sided, 0.05 level of significance. Summary statistics will be presented, as well as 95% confidence intervals (CI) on selected parameters, as described in the sections below.

6.2.2. Definition of Baseline

For all endpoints, baseline is defined as the last non-missing assessment prior to study vaccine administration. Specifically, as per the protocol, baseline evaluations are expected as follows:

- Vital signs: Day 1 prior to study vaccine administration
- Laboratory Parameters: Most recent value during Screening period (Day -30 to Day -1)
- Immunogenicity: Day 1 prior to study vaccine administration

6.2.3. Adjustments for Covariates

The randomization for Phase 1 Cohort will not be stratified.

[figure not shown]
The randomization for Phase 2 Cohort will be stratified by age group (50-59, 60-64).

Immunogenicity analyses:

- For the Analysis of variance (ANOVA), study site will be included as fixed effect in the model.
- For the Analysis of covariance (ANCOVA) and the logistic regression, study site will be included as fixed effect and the log baseline titer will be included as covariate in the model.

6.2.4. Multiple Comparisons/Multiplicity

Since there are no formal hypothesis tests in this study, no adjustment for multiplicity will be made.

6.2.6. Missing, Unused, and Spurious Data

Binary endpoints / Continuous data:

Missing data are assumed to be missing at random and ignorable. Missing data will not be estimated or imputed. Denominators for percentages will be based only on the number of subjects with non-missing values. The only exception is:

- Systemic Solicited AEs with missing “Relationship to study vaccine” will be analyzed as “Possibly related”.

Dates:

For partial or missing AE start dates the following imputation rules will be applied:

1. If year is not missing and is after the year of first dose:
 - a. If month is missing, then month will be imputed as January.
 - b. If day is missing, then day will be imputed as the first of the month.

2. If year is not missing and is the same as the year of the first dose:
 - a. If month is missing, then impute the month as the month of the first dose date.
 - b. If day is missing, and the month is the same as the month of the first dose date, then impute day as the day of the first dose date.
 - c. If day is missing but month is after the month of first dose date, then impute day as the first day of the month.
3. If year is missing, then impute the year as the year of the first dose date:
 - a. If month is missing, then impute the month as the month of the first dose date.
 - b. If day is missing, then impute the day as the day of the first dose date.
4. If the start date is completely missing, but the AE is either ongoing (i.e. AE stop date is missing) or the stop date is after the first dose date then impute the start date as the first dose date.
5. For any cases involving the rules above, if the AE end date is before the AE start date, then do not impute the AE start date and assume that the AE is treatment emergent/concomitant for the purpose of the analysis. Further, if the AE stop date occurs prior to the first dose date, do not impute the AE start date, and assume that the AE is not treatment emergent.

No imputations will be applied to AE stop dates or other dates. As indicated above, AEs with missing stop date are considered ongoing.

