#### 6.1.5 Day 29 ( $\pm$ 3 days)

The following procedures will take place during this visit:

- Concomitant medications
- AE (unsolicited) and SAE evaluation
- Biological specimen collection for clinical laboratory tests:

- Blood for hematology and chemistry
- Urine for urinalysis
- Serum for immunogenicity (subjects aged 50 to 64 years)
- [REDACTED]

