#### **6.1.6 Months 3, 4, 5, 6 (90 to 180 days after Day 1 ( $\pm$ 5 days))**

These visits are follow-up phone calls for safety evaluation. The following procedures will take place at each visit:

- SAE, NOCI, and MAAE evaluation
- Concomitant medications or vaccines potentially related to SAE, NOCI, MAAE, or prohibited medications

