6.5.1.2. Unsolicited Adverse Events

An unsolicited AE is an AE that is spontaneously reported by the subject or discovered by the Investigator. New onset of chronic illness(s) would be recorded as part of the collection of unsolicited AEs as specified in the visit procedures. Unsolicited AEs are collected separately from solicited AEs.

Solicited AEs continuing beyond 7 days will be flagged using rules given in Section 5.2 and described in separate summaries as explained in Section 6.5.1.3.

The definition of a treatment emergent AE (TEAE) is an event that occurs after vaccination and within the 28 days after vaccination (i.e., excluding those after a subject has given informed consent, but before vaccination):

- Onset (days) = Start date of AE – Date of Study Vaccine Administration + 1
- An AE is a TEAE if:
 - Onset \geq 1 and Onset \leq 28
 - For AEs with Onset=1 the time of onset of AE must be greater or equal to the time of vaccination to be considered a TEAE

Adverse events are summarized by subject, therefore, in any tabulation, a subject contributes only once to the count for a given adverse event (SOC or preferred term).

Unsolicited AEs will be coded using the Medical Dictionary for Regulatory Activities (MedDRA) and will be summarized by decreasing frequency of SOC and preferred term within SOC in the control group, as follows:

- [P] Any unsolicited TEAEs
- Possibly or probably related unsolicited TEAEs
- Unsolicited TEAEs leading to study withdrawal
- Any AE leading to death
- [P] Any SAE within 6 months after the vaccination by maximum relationship to study treatment. This summary will include serious solicited AEs.
- [P] Any NOCI within 6 months after the vaccination by maximum relationship to study treatment.
- [P] Any MAAEs within 6 months after the vaccination by maximum relationship to study treatment.

Following by-subject Listings will be provided:

- Pre-vaccination AEs (non-emergent)

- All unsolicited TEAEs
- All Serious post-vaccination AEs, NOCIs and MAAEs

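### SAP 6.2.6 rule 3 (AE start year missing) imputes the dose year and dose day whatever the known month, and so can move true in-window events out of the primary tables

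*SAP*

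**What the plan says.** SAP 6.2.6 sets out five rules for partial AE start dates.

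- **Rule 1** (year after the dose year): a missing day becomes the first of the month (1b).
- **Rule 2** (same year as dosing): a missing day in the dose month becomes the dose day (2b). For a later month, rule 2c reads "If day is missing but month is after the month of first dose date, then impute day as the first day of the month".
- **Rule 3** (year missing): the year becomes the dose year, with no check on the known month. Rule 3b adds "If day is missing, then impute the day as the day of the first dose date", again with no condition on the month.
- **Rule 4** covers a completely missing start date.
- **Rule 5** has two sentences. If the AE ends before its start date, the start is not imputed and the AE is taken as treatment emergent. If it stops before the first dose, it is taken as not treatment emergent.

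SAP 6.5.1.2 defines a TEAE as "an event that occurs after vaccination and within the 28 days after vaccination". It codes this as Onset 1 to 28, with Onset equal to the start date minus the "Date of Study Vaccine Administration + 1". The table of any unsolicited TEAE is marked as a primary summary. So are the tables of SAEs, NOCIs and MAAEs within 6 months of vaccination. AEs before vaccination go to a listing only.

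**The concern.** Membership of the primary safety tables depends on the start date, so an imputed date decides whether an event counts. Rules 2c and 3b treat the same gap differently. A missing day in the month after dosing becomes the 1st if the year was recorded, and the dose day if it was not. Losing the year adds no information about the day, so nothing justifies the switch.

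The direction matters too. Rules 1b, 2b and 2c lean early and keep a possible in-window event in the safety table. Rule 3 can do the reverse. It can take a true post-vaccination event out of the 28-day table. Across a year boundary it can also put an event among the pre-vaccination AEs, outside the 6-month SAE, NOCI and MAAE tables.

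**Working it through.** The plan gives no figure to reproduce here, so the rules themselves were run.

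**Inputs from the SAP.** Rules 1b, 2b, 2c, 3, 3b and 5 (6.2.6); Onset = start date − dose date + 1; TEAE if Onset is 1 to 28 (6.5.1.2).

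**Assumptions.** Dose dates spread evenly over a 365-day year and true onset days spread evenly. The documents give no enrolment dates.

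**Single cases, year and day missing**

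| Dose | True onset | Rule 3 date | Onset under rule 3 | Onset if the year were known |
|---|---|---|---|---|
| 20 March | 5 April (Day 17) | 20 April | 32 | 13 (1 April, rule 2c) |
| 15 December | 5 January (Day 22) | 15 January of the dose year | −333 | 18 (1 January, rule 1b) |

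In the first case the event leaves the TEAE table. In the second it is placed 334 days before vaccination.

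**Next-month events in general.** The dose day in the following month lies one month length (28 to 31 days) after the dose, so Onset is 29 to 32 and always outside the window. Of the 334 dose dates from January to November, 7 have no such day in the next month: 29, 30 and 31 January, and the 31st of March, May, August and October. Rule 3b then gives no valid date.

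**All true Day 1-28 onsets with month known, year and day missing.** There are 365 × 28 = 10,220 combinations of dose date and onset day.

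- Placed late, before rule 5: 3,972 / 10,220 = 38.9%.
- Placed before vaccination: doses from 5 to 31 December with a January onset. The number of such onset days runs from 1 to 27, so 27 × 28 / 2 = 378, and 378 / 10,220 = 3.7%.
- No valid date: 186 / 10,220 = 1.8%.

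**Effect of rule 5.** Duration is the end date minus the true start. If the end date precedes the rule 3 date, rule 5 restores the event as a TEAE.

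| Duration | Still placed late |
|---|---|
| Same day | 0% |
| 3 days | 186 / 10,220 = 1.8% |
| 7 days | 1,252 / 10,220 = 12.3% |
| 14 days | 2,694 / 10,220 = 26.4% |
| 30 days, ongoing, or no stop date | 38.9% |

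Rule 5 leaves the 3.7% as they are, because those events end after their imputed start. It leaves the 1.8% as they are, because there is no imputed start to compare.

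**After the fix.** Choosing the year that puts the known month on or after the dose month, then applying 1b/2b/2c, moves 0 of 10,220 out of the window.

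**Rules 1b/2c, for comparison.** With month and year known and the day missing, true onsets on Days 30-60 give 365 × 31 = 11,315 combinations. Of these, 5,020 (44%) are imputed to Onset 1-28.

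**The case against.** **Rule 5 already protects many of these events.** This stands. A reader might infer from rule 3b alone that a next-month event can never be a TEAE, or that all 44.4% (38.9 + 3.7 + 1.8) of such dates are lost. The documents do not support that. With a recorded end date, most short events come back through rule 5. The full late share applies only to long or ongoing events or a missing stop date.

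**Rules 1b and 2c might look like an equal error in the other direction.** They can pull events from after Day 29, when only SAEs, NOCIs and MAAEs are collected, into the 28-day table. But early imputation is a conservative convention for a safety table, and these rules move no true in-window event out. Bounding the date by the reporting contact would assume that every event is recalled at every contact. It would also need a field that the AE data items in Protocol 7.5.2 do not list. This is a trade-off, not a mistake.

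**Rule 5 might look self-contradictory.** Its two sentences overlap only when the stop date precedes dosing, and the second reads naturally as an override. It is a wording point.

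**A reader might infer bias in the VAX-24 versus PCV20 comparison.** That is not shown. The rules are the same in every arm, so absolute rates are what they mainly affect.

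**Missing years should be very rare.** Protocol 7.5.2 requires a start date for each AE, capture is electronic, and data are cleaned before each lock. This stands and limits the size, but it does not make rule 3 correct.

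**Conclusion.** Rule 3 is wrong as written. It conflicts with rule 2c, gives dates that do not exist for some dose dates, and can remove true post-vaccination events from primary safety tables. The shares above rest on evenly spread dose dates and onset days. The before-vaccination share needs doses from 5 December onward; with no December doses it is 0% and the late share is 42.5%.

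The absolute effect is small. The documents give no rate of partial dates, so no expected count can be derived. For scale, one misplaced subject moves the any-event percentage by 1/200 = 0.5 points in a Phase 2 arm and 1/16 = 6.25 points in a Phase 1 arm, and only if that subject has no other unsolicited TEAE. This is a minor correction, worth making because it concerns a pre-specified algorithm behind primary endpoints.

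**What to change.** In SAP 6.2.6:

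1. Replace rule 3 for dates with a known month: if the year is missing, choose the year that puts the known month on or after the month of vaccination and within the subject's study participation, then apply rule 1b, 2b or 2c for the day. Where no such year exists (for example, a month that falls wholly in screening), query the date.
2. Keep the first sentence of rule 5, but limit it to stop dates on or after the first dose date so that it no longer overlaps with the second. Deleting it would remove the safeguard shown above.
3. Leave rules 1b and 2c as primary. An optional sensitivity run could date events first reported after Day 29 as late as their known date parts allow.

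Items 1 and 2 cost a few lines of SAP text and derivation code and use dates already collected. Item 3 needs the contact at which each event was first reported, so availability of that field should be checked first.
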